#### 9. EFFICACY ASSESSMENT

The primary efficacy endpoint of Part 1 of this study is 1-year survival, i.e., the proportion of patients who are alive at 1-year measured from the date of the randomization. Secondary efficacy endpoints are the rate of CR, CRp, PR or CRi or hematological improvement and their corresponding durations, transfusion requirements and number of hospitalized days. The primary efficacy endpoints of Part 2 of this study are the rate of clinical benefit response (CR, CRp, PR, or major HI) and the rate of complete response (CR or CRp). Secondary efficacy endpoints are response durations, transfusion requirements, number of hospitalized days, and overall survival. The primary efficacy endpoint of Part 3 and 4 of this study is 1-year survival rate. Secondary efficacy endpoints are the rate of clinical benefit response (CR, CRp, PR, major HI or SD) and their corresponding durations, transfusion requirements, number of hospitalized days and overall survival.

The tissue samples supporting the diagnosis of AML or MDS, and the responses to sapacitabine may be submitted for central review.

Table 6 Response Criteria

Passansa Description					
Response	Description				
Complete Remission (CR) 	Normalization of peripheral neutrophils to ≥1000 /µL, platelet to ≥100,000/µL within 2 weeks of bone marrow biopsy/aspirate, and bone marrow to ≤5 % blasts; independent of transfusions*; and no extramedullary leukemia.				
Complete remission with incomplete platelet count recovery (CRp) 	Normalization of bone marrow to $\leq$ 5% blasts; peripheral neutrophils $\geq$ 1000 /µl, platelet $<$ 100,000 /µL within 2 weeks of bone marrow biopsy/aspirate; independent of transfusions*; and no extramedullary leukemia.				
Complete remission with incomplete blood count recovery (CRi) 8	Normalization of bone marrow to $\leq$ 5% blasts; peripheral neutrophils $<1000~/\mu$ L, platelet $<100,000/\mu$ L within 2 weeks of bone marrow biopsy/aspirate; independent of transfusions *; and no extramedullary leukemia.				
Partial Remission (PR) 8	Normalization of peripheral neutrophils to $\geq 1000 \ / \mu L$ , platelet to $\geq 100,000/\mu L$ within 2 weeks of bone marrow biopsy/aspirate, $\geq 50\%$ decrease in bone marrow blasts over pretreatment but still >5%; independent of transfusions * .				
Hematological improvement (HI) 9	Major response:				

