	(1) For patients with pretreatment hemoglobin < 11 g/dL, >2g/dL increase in hemoglobin; for RBC transfusion - dependent patients, transfusion - independence*				
	(2) For patients with a pretreatment platelet count <100,000/mm³, an absolute increase of ≥30,000/mm³; for platelet transfusion-dependent patients, stabilization of platelet counts and platelet transfusion independence*.				
	(3) For patients with absolute neutrophil count (ANC) $< 1,500/$ mm  before therapy, $\ge 100\%$ increase, or an absolute increase $> 500/$ mm  , whichever is greater.				
	Minor response:				
	(1) For patients with pretreatment hemoglobin < 11 g/dL, 1-2 g/dl increase in hemoglobin; for RBC transfusion – dependent patients, 50% decrease in transfusion requirements.				
	(2) Platelet response: for patients with a pretreatment platelet count $<100,000/\text{mm}^3, \ge 50\%$ increase in platelet count with a net increase $>10,000/\text{mm}^3$ but $<30,000/\text{mm}^3$ .				
	(3) For patients with absolute neutrophil count (ANC) $< 1,500/$ mm  before therapy, $\ge 100\%$ increase, but absolute increase $< 500/$ mm  .				
Stable disease (SD)**	Failure to achieve at least HI, but no evidence of clinically significant progression for > 16 weeks.				

\*independent of transfusions or transfusion –dependence refer to no packed red blood cell transfusion for 2 weeks and no platelet transfusion for 1 week .

Transfusion requirements for each patient are defined as the number of weeks during which at least one transfusion for red blood cells (RBCs) or platelets is administered and the mean number of units of RBC and platelet transfusions administered per month.

CYCLACEL LTD CONFIDENTIAL 34 of 56

\*\* for Part 2, 3 and 4 of the study only

Clinical benefit is defined as the achievement of CR, CRp, PR, major HI or SD. The duration of clinical benefit is measured from the earliest time when the patient achieved CR, CRp, PR or major HI to the first date when the major HI is lost; if the patient only achieved SD, the duration of clinical benefit is measured from the date of randomization or registration to the first date when clinically significant progression of disease is observed.

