#### 11.1.1. Screening Design

In the screening phase, a Bayesian continuous futility monitoring rule will be implemented based on the rate of CR plus CRi in each of the 3 arms of the AML stratum, respectively. An arm will be stopped if Prob (CR+CRi > 25% | data) < 0.05. The above stopping rule suggests that, given the data obtained from patients who have already been evaluated in an arm, if there is less than a 5% chance that the rate of CR+CRi is greater than 25% we will terminate the arm. This decision rule generates the following stopping boundaries, assuming a beta(1,1) prior distribution for the response (CR+CRi) rate in each arm. Stop an arm i if [ # of pts with CR or CRi in arm i / # of pts evaluated in arm i ]  $\leq$  0/10, 1/17, where i = 1, 2, or 3. The operating characteristics of this rule are shown in Table 8.

Table 8 Operating Characteristics of Futility Monitoring - Maximum 20 AML Patients

		Sample Size		
Rate of CR or CRi	Probability of stopping	P 25	P 50	P 75
0.05	0.822	10	10	17
0.10	0.54	10	17	20
0.15	0.313	17	20	20
0.20	0.165	20	20	20
0.25	0.082	20	20	20
0.30	0.039	20	20	20

After treating up to 10 evaluable AML patients defined as patients who have completed at least 1 cycle of treatment at each dosing schedule

- If no CR or CRi is observed, declare the treatment insufficiently active and no more AML patient will be treated with this dose regimen
- If at least one CR or CRi is observed, add AML patients to reach a total of 17 patients and
  - o If less than two CR plus CRi are observed, declare the treatment insufficiently active
  - o If at least two CR and CRi are observed, add AML patients to reach a maximum of 20 patients

For both AML and MDS patients, there is an early stopping rule for excessive toxicity. A dosing schedule will be declared to have excessive toxicity and no more patients will be treated with this dose regimen if among the first 10 patients treated with this dose regiment in either the AML or MDS stratum, there are > 2 patients experienced serious adverse events (excluding simple complications associated with myelosuppression such as neutropenic fever without shock or its complications from gram-negative bacteremia, anemia or mucosal bleeding, *e.g.*, epistaxis, due to thrombocytopenia easily controlled by transfusion) that are considered by investigator to be definitely, probably or possibly related to the study drug during the first two treatment cycles.

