#### 11.3.1. Screening Design

In the screening phase, a Bayesian continuous futility monitoring rule will be implemented based on the rate of clinical benefit response in each of the 3 arms, respectively. An arm will be stopped if Prob (clinical benefit response > 25% | data) < 0.05. The above stopping rule suggests that, given the data obtained from patients who have already been evaluated in an arm, if there is less than a 5% chance that the rate of clinical benefit is greater than 25% we will terminate the arm. This decision rule generates the following stopping boundaries, assuming a beta(1,1) prior distribution for the clinical benefit response rate in each arm. Stop an arm i if [# of pts with clinical benefit response in arm i /# of pts evaluated in arm i]  $\leq 0/10$ , 1/17, where i = 1, 2, or 3. The operating characteristics of this rule are shown in Table 9.

Table 9	Operating Characteristics of Futility Monitoring - Maximum 20 AML Patients in	
Part 3 and Maximum 20 MDS Patients in Part 4		

			Sample Size	
Rate of clinical benefit response	Probability of stopping	P 25	P 50	P 75
0.05	0.822	10	10	17
0.10	0.54	10	17	20
0.15	0.313	17	20	20
0.20	0.165	20	20	20
0.25	0.082	20	20	20
0.30	0.039	20	20	20

After treating up to 10 evaluable AML patients (Part 3) and 10 evaluable MDS patients (Part 4) defined as patients who have completed at least 1 cycle of treatment

- If no CR, CRp, PR, major HI or SD is observed in Part 3, declare the treatment insufficiently active and no more AML patient will be treated with this dose regimen; if no CR, CRp, PR, major HI or SD is observed in Part 4, declare the treatment insufficiently active and no more MDS patients will be treated with dose regimen;
- If at least one CR, CRp, PR, major HI or SD is observed in Part 3, add AML patients to reach a total of 17 patients and if at least one CR, CRp, PR, major HI or SD is observed in Part 4, add MDS patients to reach a total of 17 patients.
  - o If less than two CR, CRp, PR, major HI or SD are observed in Part 3, declare the treatment insufficiently active for AML preceded by MDS previously treated with hypomethylating agents; if less than two CR, CRp, PR, major HI or SD are observed in Part 4, declare the treatment insufficiently active for MDS which were previously treated with hypomethylating agents.

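### As defined, stable disease shuts out minor HI (and CRi without major HI), so some improved patients count as clinical benefit failures while unimproved patients count as successes

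*Combined protocol and SAP*

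**What the plan says.** Section 9, Table 6 lists CR, CRp, CRi, PR, HI and SD. HI has a major and a minor tier. For a transfusion-dependent patient, minor HI includes a "50% decrease in transfusion requirements"; major HI includes, "for RBC transfusion - dependent patients, transfusion - independence". SD is "Failure to achieve at least HI, but no evidence of clinically significant progression for > 16 weeks", and a footnote applies it "for Part 2, 3 and 4 of the study only".

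The text after the table states: "Clinical benefit is defined as the achievement of CR, CRp, PR, major HI or SD". The synopsis and Sections 2, 3.1, 11.2, 11.3.1 and 11.4 use the same list. Neither minor HI nor CRi is in it.

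The list drives decisions. It is a Part 2 co-primary endpoint and a secondary endpoint of Parts 3 and 4. In Section 11.3.1 it is the futility count: for example, a schedule is declared insufficiently active at 17 patients "if less than two CR, CRp, PR, major HI or SD are observed in Part 4". The same section allows expansion of a schedule with at least four such responses, subject to a limit on 30-day deaths.

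Two places use a different definition. The opening paragraph of Section 9 gives Part 2 clinical benefit without SD. The end of Section 6.2 describes clinical benefit as CR, CRi or SD.

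**The concern.** An endpoint called clinical benefit should not rank improvement below no change. Take two transfusion-dependent patients, both free of clinically significant progression beyond 16 weeks. One halves the RBC transfusion need and meets no major HI criterion; the other does not improve at all. Under Table 6 the first has achieved HI, so cannot be SD, and minor HI is not on the list: a failure. The second is SD: a success.

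At stake are the Part 2 rule and the early looks in Parts 3 and 4. Those looks turn on very small counts (0 of 10, 1 of 17), so reclassifying one or two patients can decide whether a schedule continues. The MDS and post-MDS AML patients of Parts 3 and 4 are a population in which minor blood count responses are plausible.

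**Working it through.** **Step 1. Classification.** All rows assume more than 16 weeks without clinically significant progression.

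| Best result | At least HI? | SD? | On the list? | Scored as |
|---|---|---|---|---|
| Major HI | yes | no | yes | success |
| Minor HI only | yes | no | no | failure |
| CRi, no major HI criterion met | yes (a remission listed above PR and HI) | no | no | failure |
| CRi, a major HI criterion also met | yes | no | yes, through major HI | success |
| No improvement | no | yes | yes | success |

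No other section restores minor HI. This step needs no assumption.

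**Step 2. Reproduce the plan's figures.** Inputs from Section 11.3.1: beta(1,1) prior, stop if Pr(rate > 25%) < 0.05, boundaries 0/10 and 1/17.

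- Posterior after 0/10: 0.75^11 = 0.042. After 1/17: 0.75^18 + 18 × 0.25 × 0.75^17 = 0.0395. Both boundaries reproduce.
- stop(p) = (1−p)^10 + 10p(1−p)^9 × (1−p)^7. At p = 0.30: 0.0282 + 0.1211 × 0.0824 = 0.038 (Table 9: 0.039). At p = 0.15: 0.1969 + 0.3474 × 0.3206 = 0.308 (Table 9: 0.313).

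Inputs from Section 11.2: stop at 0/12, pass at 4 or more of 24, null rate 5%, alternative 30%, both error rates 5%.

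- pass(p) = P(X24 ≥ 4) − P(X12 = 0) × P(Y12 ≥ 4), where X12 and X24 are the responses among the first 12 and all 24 patients, and Y12 those among the second 12. At p = 0.30: 0.9576 − 0.0138 × 0.5075 = 0.951. At p = 0.05: 0.0298 − 0.5404 × 0.0022 = 0.029. Both respect the stated limits.

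**Step 3. Illustrate the size.** Assumption: 30% of patients would count if minor HI and CRi were credited, and a share s of them has only minor HI, or CRi without major HI. The counted rate is then 0.30 × (1 − s). The documents give no value for s.

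| s | Counted rate | Part 2 pass | Parts 3/4 stopping, per arm |
|---|---|---|---|
| 0 | 30% | 95.1% | 3.8% |
| 1/12 | 27.5% | 92.0% | 5.6% |
| 1/6 | 25% | 87.4% | 8.1% |
| 1/4 | 22.5% | 80.9% | 11.6% |
| 1/3 | 20% | 72.2% | 16.4% |
| 1/2 | 15% | 48.2% | 30.8% |

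The one-quarter row in full: pass = 0.8220 − 0.0469 × 0.2756 = 0.809; stop = 0.0782 + 0.2269 × 0.1679 = 0.116.

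**Step 4. The other side of the fix.** Crediting these patients can also raise the counted rate of an inactive regimen. With s = 1/4, a counted 5% becomes 0.05/0.75 = 6.7%, and the Part 2 chance of passing moves from 2.9% to 0.0721 − 0.4370 × 0.0063 = 6.9%, above the 5% limit. With s = 1/2 it becomes 10%, and the chance of passing is 0.2143 − 0.2824 × 0.0256 = 20.7%.

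**The case against.** **The baseline.** The 30% activity level in Section 11.2 and the 25% threshold in Section 11.3.1 are set on clinical benefit as the protocol lists it. If the rate on that list is 30%, the Part 2 rule has its planned power. This stands: Step 3 compares two definitions and does not show that the stated design is underpowered. The shares are assumed, and nothing supports the one-half case in particular.

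**CRi.** A reader might infer that every CRi is a failure in Parts 2 to 4. The documents do not support that. CRi requires transfusion independence, and gaining independence is itself a route to major HI for a transfusion-dependent patient (with stabilized counts for platelets). Platelet or neutrophil gains can also qualify. Only CRi that meets no major HI criterion is lost. Likewise, minor HI in one lineage does not rule out major HI in another.

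**Part 1 against Part 3.** Arms A and D share a schedule, and the Part 1 AML rule counts CRi: "An arm will be stopped if Prob (CR+CRi > 25% | data) < 0.05". A reader might call this a contradiction. It is not: the populations and endpoints differ, and the Part 1 rule gives no credit for PR, HI or SD.

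**Part 2 wording.** If the opening paragraph of Section 9 governs, SD does not count in Part 2, so unimproved patients are not successes there and redefining SD changes nothing. This stands as a limit, and is a reason to reconcile the text.

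**Timing.** A patient is evaluable after one completed cycle, but SD needs more than 16 weeks. Patients moved into SD count at a look only once that time has passed, so the fix may not fully restore the 30% row.

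**Importance.** The primary endpoint of Parts 1, 3 and 4 is 1-year survival, and Part 2 can be called active on CR/CRp of at least 20% alone. Both points stand.

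**Conclusion.** The classification gap is real and follows from the text alone. A progression-free patient with only minor HI, or with CRi and no major HI criterion, is scored below a patient who did not improve. It reaches the Part 2 co-primary clinical benefit rate where SD is included (Sections 3.1, 11.2 and 11.4, and the definition after Table 6). In Parts 3 and 4 it reaches the futility screen, the expansion trigger and the secondary endpoint.

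Its size is unknown. The 81% against 95%, and 11.6% against 3.8%, hold only if the broader rate is 30% and one quarter of those patients are excluded.

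A reader might infer that the survival results are compromised. The documents do not support that: 1-year survival does not use these categories, and Part 1 does not use SD. The only link is indirect: in Parts 3 and 4 selection on survival presupposes that schedules have shown activity on clinical benefit, so a schedule could be dropped before survival is compared. The point should be corrected before clinical benefit is scored, but it is not a must-fix on the survival endpoint.

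**What to change.** In Table 6, for Parts 2, 3 and 4, define SD as: none of CR, CRp, PR or major HI reached, and more than 16 weeks free of clinically significant progression. Minor HI and CRi patients who remain progression-free then count, and the list of clinical benefit categories need not change. Apply the same wording to the Part 2 rule and the Section 11.3.1 looks.

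Reconcile the opening paragraph of Section 9 (Part 2 without SD) and the end of Section 6.2 (clinical benefit including CRi) with one definition. The sponsor should also confirm that the 5%/30% and 25% cut-offs are intended for the corrected definition, in view of the possible rise in the Part 2 false-positive chance.

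Cost: one changed sentence in Table 6, two reconciled passages and a short statement on the cut-offs. It needs no new data and no extra patients. The counted rate can only stay the same or rise; by how much cannot be said from the documents.

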### 8.1. Adverse Event Intensity and Relationship to Study Drug

An adverse event (AE) is any unfavorable and unintended sign (including an abnormal laboratory finding, for example), symptom, or disease temporally associated with the use of a medicinal product, whether or not it is considered related to treatment with the medicinal product. This includes the worsening of a pre-existing condition or the increase in frequency of a pre-existing condition. Treatment-emergent adverse events are defined as adverse events that occur after study drug administration begins through 28 days after the last dose of study drug or until the beginning of a new anticancer therapy, whichever comes first. This trial will record treatment-emergent adverse events. Adverse events that occur after the last dose of study drug, regardless of time frame, should also be reported if a casual relationship to the study drug is suspected. The NCI Common Terminology for Adverse Events (CTCAE) version 3.0 will be used to assess the severity of adverse events. Toxicities that cannot be graded using the CTCAE will be graded as grade 1 (asymptomatic), grade 2 (symptomatic but not interfering significantly with function), grade 3 (causing significant interference with function), or grade 4 (life-threatening). For this study, transfusion-dependent anemia and thrombocytopenia defined as requiring transfusion at least once per month will have a severity of grade 4.

An AE is considered serious if it meets any of the serious criteria listed in Section 8.2. To ensure no confusion or misunderstanding of the difference between the terms "serious" and "severe", which are not synonymous, the following clarification is provided:

• The term "severe" is often used to describe the intensity (severity) of a specific event (as in mild, moderate, or severe myocardial infarction); the event itself, however, may be of relatively minor medical significance (such as severe headache). This is not the same as "serious", which is based on patient/event outcome or action criteria usually associated with events that pose a threat to a patient's life or functioning. Seriousness (not severity) serves as a guide for defining regulatory reporting obligations.

All AEs will be evaluated by the Investigator for potential relationship to the study drug in the following categories:

- Definite The AE *is clearly related* to the study treatment.
- Probable The AE *is likely related* to the study treatment.

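### Major HI for red-cell-dependent patients can be scored with an unchanged transfusion need, because the independence window is 2 weeks, has no baseline comparison, and baseline dependence is not defined

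*Combined protocol and SAP*

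**What the plan says.** Table 6 in protocol Section 9 gives major HI on red cells by two routes. A patient with low pretreatment hemoglobin needs a rise of more than 2 g/dL. The other route reads "for RBC transfusion - dependent patients, transfusion - independence", with nothing further required. The platelet counterpart asks for more: "for platelet transfusion-dependent patients, stabilization of platelet counts and platelet transfusion independence". Minor HI on red cells reads "for RBC transfusion – dependent patients, 50% decrease in transfusion requirements".

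The asterisked footnote supplies the window: its terms "refer to no packed red blood cell transfusion for 2 weeks and no platelet transfusion for 1 week". It names dependence as one of the terms so defined ("independent of transfusions or transfusion –dependence refer to no packed red blood cell transfusion for 2 weeks"), although the content describes independence. Section 9 has no other statement of who counts as dependent at baseline. The text after Table 6 starts the duration of HI when the criteria are first met and sets no minimum.

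Section 8.1 has the only usable definition of dependence, given to grade adverse events: "transfusion-dependent anemia and thrombocytopenia defined as requiring transfusion at least once per month will have a severity of grade 4". It is not linked to Table 6.

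Major HI is a component of:
- clinical benefit, a Part 2 co-primary endpoint (Section 11.2);
- the Parts 3 and 4 futility and expansion rules (Section 11.3.1);
- the Part 1 MDS expansion trigger of at least 4 CR, CRp, PR and major HI (Section 11.1.1).

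**The concern.** For CR, CRp, CRi and PR the short window sits beside marrow and blood-count criteria, so it does limited harm. For red-cell HI in dependent patients it is the whole criterion. A patient whose transfusions are spaced more widely than the window meets it between any two of them, whether or not the drug has done anything.

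The same patient has had no fall in requirements and so fails minor HI. The two grades are then inverted: the better grade is the easier one to reach. At stake is whether supportive transfusion at a constant rate can add responses to the counts that decide if a regimen continues, is expanded or is called active.

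**Working it through.** **1. The plan's own figures.** Section 11.3.1 stops an arm at 0/10 or 1/17. With counted benefit rate p:

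P(stop) = (1−p)^10 + 10·p·(1−p)^9 · (1−p)^7

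At p = 0.05 this is 0.599 + 0.220 = 0.819, against 0.822 in Table 9. At 0.10, 0.15, 0.20, 0.25 and 0.30 it gives 0.534, 0.308, 0.164, 0.081 and 0.038, against 0.54, 0.313, 0.165, 0.082 and 0.039. The beta(1,1) posterior confirms that 0 responses first stops at n = 10 and 1 response at n = 17. For Part 2 (stop at 0/12, inactive at 3/24 or fewer), the exact type I error at 5% is 0.029 and the power at 30% is 0.951, consistent with the 5% error rates set in Section 11.2. The design arithmetic is sound. The question is what is counted as a response.

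**2. Fixed schedule, unchanged need.** Red cells every d days leave d − 1 free days between transfusions.
- d = 28: 27 free days, so the 14-day window is met.
- d = 15: 14 free days, met.
- d = 14: 13 free days, not met.

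Any fixed interval from 15 to 28 days is both at least monthly (Section 8.1) and independent (Table 6 footnote). The decrease in requirements is 0%, so minor HI is not met.

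**3. Both products required.** Suppose red cells and platelets are each given every 28 days. The red-cell window is satisfied on days 14 to 27 after a red-cell transfusion, which is 14 days. The platelet window fails on the day of a platelet transfusion and the next 6, which is 7 days. At least 7 days per cycle satisfy both, whatever the offset.

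**4. Irregular timing.** With Poisson transfusion times at an unchanged rate, red cells only, the simulated chance of at least one 14-day gap is:

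| Red-cell transfusions | Over 4 weeks | Over 16 weeks |
|---|---|---|
| 1 per 4 weeks | 0.91 | 1.00 |
| 1 per 2 weeks | 0.73 | 0.999 |
| 1 per week | 0.41 | 0.95 |

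**5. Effect on the decision rules.** Assume a true benefit rate of 5%, and that a share f of the other patients is counted only through this gap. The counted rate is q = 0.05 + 0.95·f. The documents do not give f. With f = 5%, q = 0.05 + 0.0475 = 9.75%. Rates of 15% and 20% correspond to f = 0.10/0.95 = 10.5% and 0.15/0.95 = 15.8%.

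The 4/24 step is the sum over x = 1 to 12 of P(X1 = x)·P(X2 ≥ 4 − x), with X1 and X2 binomial(12, q). The 30% criterion needs 11 of 36 (10/36 = 27.8%, 11/36 = 30.6%), after passing both earlier looks.

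| Counted rate q | Part 2: at least 4/24 | Part 2: at least 11/36 | Parts 3 and 4: P(stop) |
|---|---|---|---|
| 5% | 0.03 | below 0.0001 | 0.82 |
| 9.75% | 0.19 | 0.0004 | 0.55 |
| 15% | 0.48 | 0.014 | 0.31 |
| 20% | 0.72 | 0.089 | 0.16 |

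**The case against.** A reader might infer that the protocol defines dependence, for response purposes, as monthly transfusion, so that Table 6 contradicts a stated definition. It does not go that far: the Section 8.1 sentence grades anemia and thrombocytopenia and is not tied to the response criteria. If dependence simply means failing the footnote window, nobody is dependent and independent at the same moment. That objection stands as to framing, but it does not rescue the rule. A patient transfused shortly before day 1 and again 28 days later still becomes a major responder with no change in need.

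A reader might also take either product's window as sufficient, or extend the point fully to platelets. The footnote joins the two with *and*. Platelet HI also requires stable counts, although that is not quantified. Applying the joint rule with an assumed two platelet transfusions per week (not a figure from the documents) lowers the 16-week chances to about 0.96, 0.87 and 0.57.

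Stable disease (SD) overlaps with false HI. A patient without clinically significant progression for more than 16 weeks already counts as clinical benefit, so false HI adds only patients who progress or leave earlier, for whom the 4-week column is closer. This stands for Parts 3 and 4 and largely for Part 2, although the opening paragraph of Section 9 omits SD from the Part 2 endpoint. It does not apply to the Part 1 MDS expansion trigger, which excludes SD.

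Finally, Section 11.4 compares transfusion-free weeks with the 8-week baseline, so unchanged need would be visible there. That does not correct the HI count.

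**Conclusion.** The point holds for red cells. As written, the rule gives major HI to a patient on a fixed 15-to-28-day red-cell schedule with unchanged need, and denies that patient minor HI. The platelet clause is less affected. Fixed red-cell intervals of 14 days or less do not qualify, so it would be wrong to conclude that every dependent patient does.

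False major HI can enter Part 2 clinical benefit and the Parts 3 and 4 futility and expansion counts, for patients who do not reach SD. It enters the Part 1 MDS expansion trigger with no SD overlap. One-year survival, CR/CRp and the Part 1 AML futility rule on CR plus CRi are not directly affected.

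The size rests on an affected share that the documents do not give, so the table is an illustration. A reader might infer from 0.48 or 0.72 that an inactive regimen would probably be called active in Part 2. The documents do not support that: those figures cover the 4/24 step only, and the separate 30% clinical-benefit criterion would be met with probability 0.014 or 0.089. Nor does futility cease to work, since 31% of arms would still stop at a counted rate of 15%. Severity: should-fix.

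**What to change.** In Table 6, keep the 2-week and 1-week footnote for CR, CRp, CRi and PR, and correct its term to independence. For the HI clauses on dependent patients, add a separate definition:

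- Baseline dependence is set by product, from the 8-week pre-dose transfusion record already collected (Table 5, note d).
- Independence counts only if the patient is free of that product for an on-study period matched to that window (8 weeks).
- It must also be a reduction from the patient's own baseline, judged on the on-study rate and no weaker than the minor-HI requirement of a "50% decrease in transfusion requirements". Unchanged need then cannot count, and major HI is never easier than minor HI.

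The 8-week length is chosen to match the baseline window; the documents do not prescribe it. With strictly regular 4-weekly red cells it removes false HI. With randomly timed monthly need, about 0.41 of patients would still show an 8-week gap within 16 weeks (0.09 at one per 2 weeks, 0.003 at one per week), which is why the rate comparison is needed as well.

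The cost is a wording change in Table 6, with no new data, since transfusions are recorded at baseline and during follow-up. The downside is fewer and later HI responses.

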The duration of CR, CRp, PR or CRi or hematological improvement is measured from the time when response criteria are first met until the first date that recurrent or progressive disease is documented. To avoid premature discontinuation of patients who have had a temporary flare of the disease due to treatment interruptions, dose reductions, acute infection or other plausible explanations, a second assessment should be performed in these patients to confirm the recurrence or progression of disease.

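### For responders, the duration of clinical benefit ends only when major HI is lost, with recurrence, progression and death unnamed, while SD-only patients run on a different clock

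*Combined protocol and SAP*

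**What the plan says.** Section 9 (Efficacy Assessment), in the text after Table 6, defines the composite: "Clinical benefit is defined as the achievement of CR, CRp, PR, major HI or SD". It then gives this one variable two clocks.

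- Patients with CR, CRp, PR or major HI are measured from the first of these responses "to the first date when the major HI is lost".
- Patients whose only benefit is SD are measured "from the date of randomization or registration to the first date when clinically significant progression of disease is observed".

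Table 6 defines SD as "Failure to achieve at least HI, but no evidence of clinically significant progression for > 16 weeks". It makes each major HI criterion conditional on a baseline cytopenia. The platelet criterion, for example, begins "For patients with a pretreatment platelet count <100,000/mm³"; the other two require hemoglobin below 11 g/dL or ANC below 1,500/mm³.

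The next paragraph of Section 9 covers the duration of CR, CRp, PR, CRi or HI, which runs "until the first date that recurrent or progressive disease is documented".

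Section 11.4 (Data Analysis) lists Kaplan-Meier durations by category (CR, CRp, PR, CRi, HI, SD). It censors patients who leave the study for reasons other than progression at their last response evaluation. It gives no separate rule for the duration of clinical benefit.

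Clinical benefit and its durations are secondary objectives of Parts 3 and 4 (Section 2) and secondary endpoints of those Parts (Section 9).

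**The concern.** The composite has five components, but for four of them the only stated end is the loss of one, major HI. CR, CRp and PR depend on marrow blasts as well as counts. Major HI depends on counts alone, and only in patients who were cytopenic at baseline. The end event can therefore come too late (marrow relapse with preserved counts), too early (a count drifts down during remission), or never (major HI was never met).

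The two time origins add a second difficulty. SD-only patients are credited with the time from study entry, and responders are not credited with the time before their response.

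At stake is whether the reported durations mean the same thing from patient to patient, and whether two analysts would obtain the same values from the same data.

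**Working it through.** The plan states no figure for this endpoint, so there is none to reproduce. The check sets the rules side by side and applies them to illustrative patients. **All dates and blood counts below are assumptions, not values from the documents.**

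| Rule | Start | End |
|---|---|---|
| Clinical benefit, responders (Section 9) | First CR, CRp, PR or major HI | Loss of major HI |
| Clinical benefit, SD only (Section 9) | Randomization or registration | Clinically significant progression |
| CR, CRp, PR, CRi, HI (Section 9, next paragraph) | Criteria first met | Recurrence or progression |

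**1. End too late.** CR at week 8, marrow relapse at week 20, major HI lost at week 28.
- CR duration: 20 − 8 = 12 weeks.
- Clinical benefit duration: 28 − 8 = 20 weeks, of which 28 − 20 = 8 weeks follow the relapse.
- If the counts fall at relapse, the excess is 20 − 20 = 0 weeks.

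Such a patient need not leave the study at relapse. Section 4.3 defines clinically significant progression as a blast increase of more than 50% over baseline, reaching at least 20%. With 30% blasts at baseline, the threshold is 30% × 1.5 = 45%, so a relapse from remission to 25% does not meet it.

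**2. End too early.** A CR patient's platelets rise from 90,000 to 125,000. The gain is 35,000, which meets the major HI threshold of 30,000. They then fall to 110,000, a gain of 20,000, so major HI is lost. If neutrophils and marrow still qualify, the patient remains in CR, because platelets are at least 100,000. If platelets were the only HI lineage, clinical benefit ends during remission.

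**3. No end date.** A CRp patient is not transfusion-dependent at baseline and has:
- baseline hemoglobin 11.5 g/dL, so the hemoglobin criterion does not apply;
- ANC 1,200 rising to 1,500, a gain of 300 (25%), below both the 100% and the 500/mm³ thresholds;
- platelets 60,000 rising to 80,000, a gain of 20,000, below 30,000.

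CRp is met (ANC at least 1,000, platelets below 100,000), but major HI never is. There is no date on which it can be lost.

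**4. Two origins.** Two patients both reach their end event at week 20. The SD-only patient is credited with 20 − 0 = 20 weeks. A patient with PR at week 8 is credited with 20 − 8 = 12 weeks. The gap of 8 weeks is the time to response. By definition an SD-only patient must also exceed 16 weeks, while responders have no minimum.

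**5. Does Section 11.4 repair this?** It says who is censored, not what ends clinical benefit. If its censoring sentence is applied to this variable, a responder who stops for progression with major HI intact is not censored by Section 11.4 and has no end event under Section 9.

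**The case against.** The strongest reply has four parts.

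- **The two paragraphs define different variables.** This stands. Response duration already ends at recurrence or progression. A reader might infer that the paragraphs contradict each other, but the documents do not support that. The gap lies in the clinical benefit variable alone.
- **Loss of major HI may be a deliberate hierarchy.** Major HI by itself counts as clinical benefit, so a patient who falls from CR to major HI could fairly be said still to benefit. This has force, and it argues against ending benefit whenever the best response is lost. It does not explain benefit ending during a remission, or the responder with no end date, and the plan does not state it as the intention.
- **No pooled analysis is named.** This stands. Section 11.4 lists durations by category, with SD on its own. A reader might infer that the durations cannot be pooled and that a planned analysis is therefore invalid. The documents do not go that far: the different origins do not disturb category-specific estimates, and they matter only if SD-only and responder durations are combined.
- **Post-relapse accrual is bounded.** This stands. A reader might infer that it is unlimited. It lasts only until major HI is lost or follow-up is censored, and Section 4.3 ends participation for progression or lack of efficacy. How often major HI outlasts a relapse cannot be determined from the documents.

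**Conclusion.** The definition needs correction. Taken literally, the responder rule can run past relapse or progression, can stop during remission, and can leave a responder without an end date. Neither the adjacent paragraph nor Section 11.4 closes these gaps for a stated secondary endpoint of Parts 3 and 4.

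The size is uncertain. The 8-week excess and the 8-week difference in origin follow from assumed dates. The excess ranges from 0 upward with the time for which major HI survives relapse, and the difference in origin equals the time to response. The case without an end date needs a responder who meets no major HI criterion in any lineage, which may be uncommon.

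A reader might infer that an arm with more SD could be preferred because of longer apparent benefit. The documents do not support this. In Parts 3 and 4, arms are screened on the clinical benefit rate and selected on 1-year survival; Part 2 decisions rest on response rates. No primary endpoint, stopping rule, arm selection or sample size is affected.

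**What to change.** In Section 9:

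1. End the duration of clinical benefit for every patient at the earliest of documented recurrence or progression, loss of all qualifying benefit (for a responder, no longer meeting CR, CRp, PR or major HI), or death. A patient who drops from CR to major HI without documented recurrence then continues to count, and a responder who never had major HI gets an end date.
2. Either use one time origin for clinical benefit (randomization, or registration in Part 2), or state that SD-only durations are reported separately and not combined with those of responders. A common origin alone does not remove the 16-week minimum built into SD, so separate reporting is the clearer choice if the categories are to be compared.
3. Align this definition with the response-duration paragraph of Section 9 and with the Kaplan-Meier and censoring text of Section 11.4, which should name the duration of clinical benefit if it is to be analyzed.

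The cost is a few sentences. The changes use data already collected and need no new assessments. Some reported durations will become shorter.
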